8.2.2 Secondary Efficacy Endpoints

The secondary endpoint PGIC at Week 26 will be analyzed using the similar model as specified for the primary analysis (MMRM) replacing the average daily sunlight exposure time to first prodromal symptom baseline covariate with PGIS covariates at baseline visit.

The change from baseline for total score in each domain of physical function and pain intensity in the PROMIS-57 at Week 26 will be analyzed in the same way.

For the total number of sunlight-induced pain events defined as prodromal symptoms with pain rating of 1-10 on the Likert scale during the 26-week double-blind treatment period, the negative binomial regression model with log link will be used. The model will include treatment and the randomization stratification factors as fixed effect. The estimated incidence rate (IR) and its 95% confidence interval for each treatment group, incidence rate ratio (IRR) of each active MT-7117 treatment group versus placebo, 95% confidence interval of the IRR together

with relevant p-values will be reported.

The following example SAS code will be used;

[REDACTED]

The percentage of subjects who are responders based on average daily sunlight exposure time to first prodromal symptom associated with sunlight exposure between 1 hour post sunrise and 1 hour pre-sunset defined by within-subject meaningful change of 66 minutes increase from baseline to Week 26, will be analyzed using logistic regression analysis. The model will include the treatment group and the randomization stratification factors as fixed effect and the baseline average daily sunlight exposure time to first prodromal symptom as covariate. The treatment odds ratio at Week 26 will be estimated using a contrast. The missing data at Week 26 due to no available average daily sunlight exposure time to first prodromal symptom will be addressed as non-responder.

For each secondary efficacy endpoint, a subgroup analysis by region (North America, Europe, Japan, Australia) will be done.

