14.3.2.2 Analysis of Secondary and Other Efficacy Endpoints

The following secondary and other efficacy endpoints will be analyzed using the MMRM similar to the analyses for the primary endpoint.

- Secondary Efficacy Endpoint) PGIC at Week 26.
- Change from baseline in the average daily mean intensity on an 11-point Likert scale of the subject's prodromal symptoms over time during 26-week double-blind treatment period.
- Change from baseline in average daily duration (minutes) of prodromal symptoms during 26-week double-blind treatment period.
- Change from baseline in the average daily mean intensity of the subject's phototoxic reactions (associated with sun exposure) during 26-week double-blind treatment period on an 11-point Likert scale.
- Change from baseline in average daily duration (minutes) of phototoxic reactions (associated with sun exposure) during 26-week double-blind treatment period.
- Secondary Efficacy Endpoint*) Change from baseline for all total score and total score in each domain of physical function*, anxiety, depression, fatigue, sleep disturbance, ability to participate in social roles and activities, and pain interference (including pain intensity*) in PROMIS-57.
- Change from baseline in PGIS at each visit.

The following secondary efficacy endpoints and exploratory efficacy endpoint will be analyzed; a negative binomial regression model with log link will be fitted. The model will include treatment as fixed effect, and baseline total number of sunlight exposure episodes with prodromal symptoms as the covariate. The estimated incidence rate (IR) and its 95% confidence interval for each treatment group, incidence rate ratio (IRR) of each active MT-7117 treatment group versus placebo, 95% confidence interval of the IRR together with relevant p-values will be reported.

- Secondary Efficacy Endpoint) Total number of sunlight-induced pain events defined as prodromal symptoms (burning, tingling, itching, or stinging) during 26-week double-blind treatment period.
- Total number of sunlight-induced pain events defined as phototoxic events during 26-week double-blind treatment.
- Total number of sunlight-induced non-prodrome, phototoxic reactions during 26-week double-blind treatment.

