1 INTRODUCTION

This statistical analysis plan (SAP) is based on the final global master protocol version 4.1 dated 9AUG2021, the final Japan specific protocol (v4.2) dated 24 August 2021, and the final Norway specific protocol (v4.3) dated 24 August 2021, and the final Germany specific protocol (v4.4) dated 24 August 2021 and , and the final Canada specific protocol (v4.5) dated 24 August 2021. The plan covers statistical analysis, tabulations, and listings of the study data to assess the efficacy, safety, and PK of [REDACTED] and [REDACTED] doses of MT-7117 compared to placebo.

Any statistical analysis details described in this document supersede any description of statistical analysis in the protocol.

The SAP is prepared by MTD A and MTPC data science and reviewed by MTD A clinical study team and MTPC data science following GLB-BST-SOP002 ver.7. The statistical analyses and production of the outputs described in the SAP will be conducted and QCed by [REDACTED]
[REDACTED] using SAS version 9.4 or higher. The final analyses and outputs will be approved by MTPC/MTD A Data Science.

This SAP has been approved and signed as Version 1.0 and Version 1.1 for FDA SAP communication. Version 2.0 will be finalized for the Primary Week 26 analysis prior to Week 26 database lock, and Version 3.0 will be finalized for the final analysis prior to the final database lock.

The analysis plan for the PPKPD will be described in a separate document and the results will be separately reported.

For the qualitative exit interview questionnaire, the analysis plan , the dataset and the results will be separately created and reported.

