6.3 Stratification registration errors

All patients enrolled into this study were randomized into the IWRS system based on Bracket IRT Randomization List Requirements. [REDACTED]

[REDACTED] in the [REDACTED] system was not consistent with a vendor [REDACTED] report strata and actual baseline TTP strata based on the e-Diary in some

patients. Therefore, it is planned to summarize the status of randomization factor registration error in the section of stratification registration errors and perform the sensitivity analysis for the primary efficacy endpoint to investigate the impact by the errors for study outcome.

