8.1.5 Demographic and Other Baseline Characteristics

The following demographic and other baseline characteristics will be used.

	Category	Descriptive
Sex	Male, Female	
Age (years)	Adolescent(<18) Adult(18 – 65, >65)	Yes
Height (cm) at screening visit		Yes
Weight (kg) at screening visit	<45 ≥45	Yes
BMI (kg/m2)	[REDACTED]	Yes
Race	White, Black or African American, Asian(Japanese), American Indian or Alaska Native, Native Hawaiian or Pacific Islander, Other	
Country	US, Australia, Canada, Germany, Italy, Japan, Norway, Spain, Sweden, United Kingdom (from IWRS data)	
Region (Randomization stratification factor)	North America, Rest of world (Europe, Japan, Australia) (from IWRS data)	
Ethnicity	Hispanic or Latino, Non-Hispanic or Latino	
EPP/XLP	EPP, XLP	
Protoporphyrin (PPIX level) (mcg/dL)		Yes
Disease duration (years)		Yes
Baseline average daily time to first prodromal symptom (Randomization stratification factor)	[REDACTED]	
Actual baseline average daily time to first prodromal symptom	[REDACTED] [REDACTED]	Yes
Seasonality 1	Randomized in Spring and Summer inclusive, Other	

	(Spring and Summer: between September 1st to February 29 in Australia or between March 1st and August 31th in the other countries)	
Seasonality 2	Week 26 visit in Spring and Summer inclusive, Other (Spring and Summer: the date of Week 26 analysis visit is between September 1st and February 29th in Australia or the date of Week 26 analysis visit is between Mar 1st and August 31th in the other countries)	
Melanin density		Yes
Fitzpatrick skin type	I, II, III, IV, V-VI	
		

Demographic and other baseline characteristics will be summarized on the ITT1, ITT2, SAF1, and SAF2 populations. Demographic and other baseline characteristics will be summarized on the ITT1, ITT2, SAF1, and SAF2 populations by region (North America, Europe, Japan, Australia).

Demographic and other baseline characteristics will be listed on the RAND population.

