10 CHANGE FROM THE PROTOCOL

There are currently no changes to analysis from protocol.

[figure not shown]
[figure not shown]

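### SAP 10 declares no change from the protocol, yet the model it lists for the confirmatory pain-event count (H5/H6) adds the randomization strata and no longer names the baseline episode count

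*SAP*

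**What the plan says.** Protocol 14.3.2.2 puts the count of prodromal pain events and two phototoxic counts under one negative binomial model: "The model will include treatment as fixed effect, and baseline total number of sunlight exposure episodes with prodromal symptoms as the covariate". It lists no randomization strata. The protocol synopsis names the negative binomial model but gives no terms.

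SAP 8.2.2 keeps the negative binomial model with log link for the prodromal pain-event count and describes it so: "The model will include treatment and the randomization stratification factors as fixed effect". No baseline covariate appears in the visible text, and the example code that follows is redacted. SAP 8.2.3 applies the same model to the two phototoxic counts.

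On precedence, SAP 1 says: "Any statistical analysis details described in this document supersede any description of statistical analysis in the protocol". On differences, SAP 10 says: "There are currently no changes to analysis from protocol".

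SAP 8.1.5 marks two variables as stratification factors: region, and baseline average daily time to first prodromal symptom. SAP 6.3 reports that a stratum record did not agree with the vendor "report strata and actual baseline TTP strata based on the e-Diary in some" patients. Its response is to summarize the errors and to "perform the sensitivity analysis for the primary efficacy endpoint to investigate the impact by the errors for study outcome".

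**The concern.** The pain-event count is a confirmatory endpoint, fifth and sixth in a fixed sequence of twelve hypotheses. If H5 fails, the seven hypotheses H6 to H12 lose their formal test. The model for such an endpoint should be traceable from protocol to SAP. Here a reader who relies on SAP 10 is told that nothing changed, although the listed terms did.

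Two consequences follow if the visible text is complete. First, any baseline adjustment for H5/H6 comes from the strata alone. One stratum is a categorized time to first symptom, which is related to an episode count but is not one. Second, that stratum is the one SAP 6.3 reports as inconsistent in some patients, and the planned check with actual strata covers only the primary endpoint.

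**Working it through.** **Model terms side by side**

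| Place | Treatment | Randomization strata | Baseline episode count |
|---|---|---|---|
| Protocol synopsis | no terms listed | no terms listed | no terms listed |
| Protocol 14.3.2.2 | yes | not listed | yes |
| SAP 8.2.2, visible text | yes | yes | not listed |
| SAP 8.2.3, two phototoxic counts | as 8.2.2 | as 8.2.2 | as 8.2.2 |

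Two of the three terms differ between the protocol body and the SAP. SAP 10 lists neither difference.

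**Is the omission shorthand?** Probably not. The next model in SAP 8.2.2, for responders, names treatment, the strata and "the baseline average daily sunlight exposure time to first prodromal symptom as covariate". SAP 8.2.3 says explicitly that the total-time endpoints take no baseline covariate. So the SAP tends to write a covariate out when it wants one. SAP 7.2.2.3.4 also derives the event count only from the baseline date onward; no baseline episode count is derived in the visible text.

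**Size.** The plan gives no event rate, dispersion, effect or power for H5/H6, so there is no figure to reproduce. The following simulation is illustrative, and every input except the arm size is assumed:

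- 61 per arm (184/3 = 61.3), incidence rate ratio 0.65, two-sided 5% Wald test.
- Gamma-distributed subject rates; a 14-day baseline count, entered untransformed.
- Baseline-time stratum explains 10% and region 5% of log-rate variance.
- 4,000 replicates per setting; strata correctly registered in this table.

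| Dispersion; events/day | Correlation | Protocol model | SAP model | Strata + count | SAP minus protocol | Gain from adding count |
|---|---|---|---|---|---|---|
| 0.5; 0.1 | 0.3 | 83.1% | 87.8% | 88.1% | +4.7 | +0.3 |
| 0.5; 0.1 | 0.5 | 84.4% | 86.9% | 88.3% | +2.5 | +1.4 |
| 0.5; 0.1 | 0.7 | 87.7% | 87.8% | 91.0% | +0.1 | +3.2 |
| 1; 0.3 | 0.3 | 58.2% | 65.0% | 64.8% | +6.8 | -0.2 |
| 1; 0.3 | 0.5 | 61.9% | 66.1% | 68.7% | +4.2 | +2.6 |
| 1; 0.3 | 0.7 | 67.8% | 64.4% | 72.9% | -3.4 | +8.5 |

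Over all settings with correct strata, adding the count changes power by -0.4 to +0.3 points when baseline does not predict later counts or the correlation is 0.3. The gain is 1.4 to 2.6 points at 0.5 and 3.2 to 8.5 at 0.7. With an assumed 10 to 20% of baseline-time strata misregistered, the gains at 0.3, 0.5 and 0.7 are 0 to 0.9, 1.9 to 4.2 and 3.0 to 9.6 points. SAP 6.3 gives no misregistration rate.

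**What the correlation means.** For two counts sharing one gamma rate with dispersion k and means m1 and m2, the observed correlation is k·m1·m2 / √[(m1 + k·m1²)(m2 + k·m2²)]. At 0.1 events/day, m1 = 14 × 0.1 = 1.4 and m2 = 182 × 0.1 = 18.2. With k = 0.5 this gives 12.74 / √(2.38 × 183.82) = 12.74 / 20.92 = 0.61. A value of 0.7 therefore cannot be an observed count correlation in that setting. The column has to be read as correlation of the underlying rates.

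**Test size.** Under a true null the SAP model rejects 5.6 to 7.4% of the time and the model with the count 5.7 to 7.2%. Adding the count does not inflate the error relative to the SAP model, but the powers above are not at exactly nominal size.

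**The case against.** The strongest reply is that nothing is left open. The protocol describes its statistical section as the basis for the SAP and allows revision, SAP 1 gives the SAP precedence, and so one visible specification governs. This stands as far as it goes: the model to be run is settled. It does not make the statement in SAP 10 true.

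Three stronger readings are tempting, and the documents do not support them.

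- *The covariate was removed.* The example code directly after the model description is redacted, and a baseline term there cannot be excluded. The contrast with the responder model makes omission likely, not certain. If the code does hold the covariate, the text of 8.2.2 still needs correcting.
- *The SAP model is inferior to the protocol's.* In five of the six rows above it has equal or higher power. The gains in the last column compare it with a third model, strata plus count, which neither document specifies. The ordering depends on the assumptions: a smaller run (400 replicates, rate ratio 0.6, log baseline count, baseline rate largely carried over) favoured the baseline-count model, with power of 81 to 97% against 71 to 90%.
- *The comparison is biased.* Omitting a prognostic baseline covariate does not bias the randomized comparison. At most it costs precision.

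It is also fair to say that the time for changing the confirmatory model has probably passed. SAP 7 describes the review meetings for both the Week 26 and the final analysis in the past tense.

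**Conclusion.** The point holds as a discrepancy in documentation and traceability for a confirmatory endpoint. The listed terms for H5/H6 differ from the protocol in two respects, SAP 10 says there is no difference, and the two exploratory phototoxic counts carry the same discrepancy. This rests on the text alone and needs no simulation; its one limit is the redacted code.

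The effect on power cannot be derived from the documents. Under the stated assumptions, a model with both strata and the baseline count gains about nothing when the underlying rates are weakly correlated and a few points when the correlation is moderate to high. These figures illustrate a possible benefit; they do not estimate a loss caused by the SAP.

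A separate gap also stands: the reported stratum errors affect a term in the H5/H6 model, but the analysis with actual strata is planned only for the primary endpoint.

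**What to change.** 1. Correct SAP 10 to list the H5/H6 difference, with the reason: randomization strata added, baseline episode count not among the listed terms. Note that the SAP 8.2.3 phototoxic counts follow the same model.
2. If Week 26 data are still blinded, specify treatment, randomization strata and the protocol's baseline episode count in SAP 8.2.2 and for the 8.2.3 counts. If they are already unblinded, as SAP 7 suggests, keep the SAP model as the confirmatory test and report the model with the baseline count as a sensitivity analysis. Either way, state how the baseline count is derived, because Protocol 14.3.2.2 gives no window for it. The general 14-day diary window in Protocol 6.2.1 is the obvious source.
3. Extend the actual-strata sensitivity analysis to H5 and H6.

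The cost is a few lines of SAP text, one model term or one extra model fit, and one further sensitivity run. No new data are needed: Protocol 11.5 already required at least 7 days of outside exposure data in the 14 days before randomization.

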8.2.3 Exploratory Efficacy Endpoints

The following exploratory efficacy endpoints will be analysed using the similar model as specified for the primary analysis (MMRM) replacing the baseline average daily sunlight exposure time to first prodromal symptom as covariate with the corresponding covariates at baseline visit in the below bullets.

- Change from baseline in the average daily mean intensity on an 11-point Likert scale of the subject's prodromal symptoms over time during 26-week double-blind treatment period.
- Change from baseline in average daily duration (minutes) of prodromal symptoms during 26-week double-blind treatment period.

- Change from baseline in the average daily mean intensity of the subject's phototoxic reactions (associated with sun exposure) during 26-week double-blind treatment period on an 11-point Likert scale.
- Change from baseline in average daily duration (minutes) of phototoxic reactions (associated with sun exposure) during 26-week double-blind treatment period.
- Change from baseline for all total score and total score in each domain of, anxiety, depression, fatigue, sleep disturbance, ability to participate in social roles and activities, and pain interference in the PROMIS-57
- Change from baseline in PGIS at each visit.

The following endpoints will be analysed using the same negative binomial model with log link as specified for the secondary efficacy endpoint.

- Total number of sunlight-induced pain events defined as phototoxic events during 26-week double-blind treatment.
- Total number of sunlight-induced non-prodrome, phototoxic reactions during 26-week double-blind treatment.

The following endpoint will be analysed using the same logistic regression model as specified for the secondary efficacy endpoint.

- The percentage of subjects who are responders at Week 26 based on PGIC (Very Much Improved or Much Improved).

The following endpoint will be listed and summarized by treatment and planned time point using descriptive statistics. The value of melanin density, change from baseline and % change from baseline in melanin density at each visit by skin segments and average of 6 skin segments will be plotted by treatment. The average of 6 skin segments for the melanin density and for the change from baseline in melanin density at each visit, will be analysed using MMRM model similar to the analyses for the primary endpoint. A subgroup analysis by region (North America, Europe, Japan, Australia), by Fitzpatrick scale test category (I-II or III-VI), by Melanin density at BL (\geq Median, $<$ Median) and by the [REDACTED] will be done.

- Change from baseline and % change from baseline in melanin density at each visit by skin segments. Average of 6 skin segments for the change from baseline and % change from baseline in melanin density at each visit.

The following endpoints will be analysed using either ANCOVA or ANOVA model. The ANCOVA model will include the treatment group, randomization strata as fixed factors together with continuous covariate terms for the corresponding baseline values except for the below total

time endpoints.

- Change from baseline for in-clinic sunlight exposure time (minutes) to the first prodromal symptoms or end of test, whichever comes first.
- Total time (hours) during the 26-week double-blind treatment period in duration of sunlight exposure between 1 hour post sunrise and 1 hour pre-sunset without prodromal symptoms.
- Total time (hours) during the 26-week double-blind treatment period in duration of sunlight exposure between 1 hour post sunrise and 1 hour pre-sunset without prodromal symptom with the severity of greater than 0 on 11-point Likert scale and without phototoxic reactions (pain-free time hours).
- Change from baseline in average daily duration of sunlight exposure regardless of time of day without prodromal symptoms assessed at Week 26.

The following endpoints will be summarized using descriptive statistics and Wilcoxon's rank sum test.

- Total number of days subject is exposed to sunlight for any duration without prodromal symptoms during 26-week double-blind treatment period.
- Total number of days subject is exposed to sunlight for any duration without prodromal symptom with the severity of greater than 0 on 11-point Likert scale and without phototoxic reactions (pain-free days) during the 26-week double-blind treatment period.
- Total number of days subjects went outdoors during the 26-week double-blind treatment period.
- Total severity of phototoxic reaction on an 11-point Likert scale during the 26-week double-blind treatment period

Maximum severity of phototoxic reaction on an 11-point likert scales will be summarized using frequency and percentage. Shift table of maximum phototoxic reaction on an 11-point Likert scale at Week 26 or EOT will be presented using frequnecye and perenctage.

For DBE data analysis

All efficacy endpoints in Section 2.3.4 will be simply and descriptively summarized in the ITT2 population in the above similar approach without statistical models.

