The following efficacy endpoints will be analyzed; a logistic regression model will be fitted. The model will include the treatment group, randomization strata as fixed factors together with continuous covariate term for the corresponding baseline value. The treatment odds ratio at Week 26 and its 95% confidence interval with p-value for each treatment group will be estimated using a contrast.

- Secondary Efficacy Endpoint) The percentage of subjects who are responders based on average daily sunlight exposure time to first prodromal symptom associated with sunlight

- exposure between 1 hour post-sunrise and 1 hour pre-sunset defined by within-subject meaningful change of 66 minutes increase from baseline to Week 26.
- The percentage of subjects who are responders at Week 26 based on PGIC (Very Much Improved or Much Improved).

The following other efficacy endpoint will be listed and summarized by treatment and planned time point using descriptive statistics. The value of melanin density, change from baseline, and % change from baseline in melanin density at each visit by skin segments and average of 6 skin segments will be plotted by treatment. For average of 6 skin segments for the value of melanin density, change from baseline in melanin density at each visit, will be analyzed using MMRM similar to the analyses for the primary endpoint.

- Change from baseline and % change from baseline in melanin density at each visit by skin segments. Average of 6 skin segments for the change from baseline and % change from baseline in melanin density at each visit.

The following endpoint will be analyzed using ANCOVA or ANOVA model:

- Change from baseline for in-clinic sunlight exposure time (minutes) to the first prodromal symptoms or end of test, whichever comes first.
- Total time (hours) during the 26-week double-blind treatment period in duration of sunlight exposure between 1 hour post-sunrise and 1 hour pre-sunset without prodromal symptoms.
- Total time (hours) during the 26-week double-blind treatment period in duration of sunlight exposure between 1 hour post-sunrise and 1 hour pre-sunset without prodromal symptom with the severity of greater than 0 on 11-point Likert scale and without phototoxic reactions (pain-free time hours).
- Change from baseline in average daily duration of sunlight exposure regardless of time of day without prodromal symptoms assessed at Week 26.

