8.2.1 Primary Efficacy Endpoint

Primary Analysis

For the ITT1 population, the primary estimand will be tested including retrieved dropout data (after treatment discontinuation), using treatment comparisons of interest in change from baseline in average daily time to first prodromal symptom associated with exposure to sunlight between 1 hour post sunrise and 1 hour pre-sunset for the two MT-7117 doses (█ and █ █) compared with placebo at Week 26 (Visit 7).

To assess the treatment effect at Week 26, change from baseline in average daily time (minutes) to first prodromal symptom associated with exposure to sunlight between 1 hour post sunrise and 1 hour pre-sunset at Weeks 2, 4, 6, 8, 10, 12, 14, 16, 18, 20, 22, 24, and 26 will be analyzed using mixed-effect model for repeated measures (MMRM). The model will include fixed categorical terms for treatment, █

█ visit, and treatment by visit interaction together with continuous covariate terms for baseline average daily duration of sunlight exposure between 1 hour post sunrise and 1 hour pre-sunset to first prodromal symptom and baseline average daily duration of sunlight exposure between 1 hour post sunrise and 1 hour pre-sunset to first prodromal symptom by visit interaction. An unstructured (UN) correlation structure will be used to model the within-subject variance covariance errors. Should convergence of the model fail (due to the small numbers of

subjects in this study), the heterogeneous compound symmetry (CSH) and the heterogeneous Toeplitz structure (TOEPH), autoregressive [AR(1)] and compound symmetry (CS) correlation matrix will be used in that order instead of UN. The Kenward-Roger approximation will be used to estimate the denominator degrees of freedom. From the model described above, adjusted (least squares [LS]) means and standard errors will be produced by treatment group and visit. Difference in adjusted means at each visit (each MT-7117 dose vs. placebo) with standard errors, 95% CIs and associated p-values will also be produced. All available data from all subjects will be used in the primary analysis without any imputation.

Sensitivity Analysis

(1) Use of actual strata of baseline average daily sunlight exposure time to first prodromal symptom for randomization registration errors

In the above primary analysis model, [REDACTED]

[REDACTED] directly derived from e-Diary raw dataset.

(2) Controlled multiple imputation method

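### The melanin-density MMRM is not given a melanin baseline: read literally, the raw-value model is imprecise and can disagree with the change-from-baseline model (minor, exploratory endpoint)

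*SAP*

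**What the plan says.** SAP 8.2.3 gives melanin density its own paragraph, covering listings, plots, a model and subgroup analyses. Two outcomes enter the model: "The average of 6 skin segments for the melanin density and for the change from baseline in melanin density at each visit". Both, "at each visit, will be analysed using MMRM model similar to the analyses for the primary endpoint". No covariate is named there.

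The primary model in SAP 8.2.1 contains "continuous covariate terms for baseline average daily duration of sunlight exposure between 1 hour post sunrise and 1 hour pre-sunset to first prodromal symptom", together with the interaction of that baseline with visit. Some of its categorical terms are redacted, but the continuous ones are visible.

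SAP 8.2.3 opens with a substitution rule for a group of MMRM endpoints, "replacing the baseline average daily sunlight exposure time to first prodromal symptom as covariate with the corresponding covariates at baseline visit in the below bullets". The six bullets are prodrome intensity, prodrome duration, phototoxic-reaction intensity, phototoxic-reaction duration, PROMIS-57 scores and PGIS. Melanin density is not among them. After the melanin paragraph, the ANCOVA endpoints are given "continuous covariate terms for the corresponding baseline values", apart from the total-time endpoints.

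Protocol 14.3.2.2 has the same structure: "For average of 6 skin segments for the value of melanin density, change from baseline in melanin density at each visit", an MMRM like the primary one, and no covariate named. Protocol 7.1 has melanin density measured before randomisation, so the baseline exists. SAP 8.2.3 itself uses it as a median-split subgroup factor.

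**The concern.** A programmer who follows the text to the letter would adjust skin pigmentation for baseline minutes to first prodrome and leave out baseline pigmentation. The raw-value comparison would then carry all of the between-subject spread in skin colour that a baseline term would remove. It would also carry any chance difference in baseline skin colour between arms.

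The planned pair of outcomes adds a second difficulty. Without the baseline term, the raw-value and change models estimate the treatment difference differently. The SAP would produce two differences and two p-values for one question, with no rule on which is to be cited. The effect on melanin density is a stated exploratory objective, and Protocol 7.2 uses it to assess the drug's effect on pigmentation, so the result is likely to be read.

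**Working it through.** **What the documents supply.** They give about 61 subjects per arm (Protocol 8.1) and a two-sided 5% level (SAP 6.2). They give no SD, no correlation and no power for melanin density, so there is no melanin figure to reproduce. The stated sample size concerns the primary endpoint only and is unaffected by this point. It does reproduce: 42 completers per arm, 57 min and SD 79.3 give 91%; a fixed-sequence simulation adding the 52 min comparison gives 79% for both; and 42/0.8, rounded up, is 53 per arm, or 159.

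**Assumptions.** The SD is the same at baseline and Week 26 and is set to 1. The baseline to Week 26 correlation r is shown over a range. One visit is considered, and baseline time to prodrome is taken as uncorrelated with melanin density.

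**Precision.** The variance of the treatment contrast is proportional to:

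- raw value, no melanin baseline: 1
- change from baseline, no melanin baseline: 2(1 − r)
- adjusted for baseline melanin: 1 − r²

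The SE relative to the adjusted model is therefore 1/√(1 − r²) for the raw value and √(2/(1 + r)) for change. The power columns use 61 per arm and an effect δ = (1.96 + 0.842) × √(1 − r²) × √(2/61), which has 80% power in the adjusted model.

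| r | SE ratio, raw | SE ratio, change | Power, raw | Power, change |
|---|---|---|---|---|
| 0.5 | 1.15 | 1.15 | 68% | 68% |
| 0.7 | 1.40 | 1.08 | 52% | 73% |
| 0.8 | 1.67 | 1.05 | 39% | 76% |
| 0.9 | 2.29 | 1.03 | 23% | 78% |

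For example, at r = 0.8: 1 − r² = 0.36, so the raw-value SE ratio is 1/0.6 = 1.67. The effect is δ = 2.802 × 0.6 × 0.181 = 0.304 SD, and raw-value power is Φ(0.304/0.181 − 1.96) = Φ(−0.28) = 39%.

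**Chance baseline gap.** With 61 per arm, the difference in baseline means has SE √(2/61) = 0.181 SD, and 1.96 × 0.181 = 0.355 SD. Given an observed gap d, the expected error is r·d for the raw value, −(1 − r)·d for change, and 0 when adjusted. With d = 0.3 SD and r = 0.8 these are +0.24, −0.06 and 0 SD; a simulation of 40,000 null trials gave +0.23, −0.06 and 0.00. Over all randomisations in that simulation no estimator was biased, and type I error was 5.2% (raw) and 5.0% (change).

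**Why one model suffices.** Suppose baseline melanin and its visit interaction are both in the model. Subtracting the baseline from the outcome then only lowers the baseline slope at each visit by 1. The treatment contrast, its SE and its p-value are the same for value and for change.

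**The case against.** The strongest reply is that the SAP never says melanin keeps baseline time to prodrome. It says the model is similar to the primary one, and in the primary model the continuous covariate is the outcome's own baseline, so the natural analogue is baseline melanin. The protocol uses nearly the same wording for PGIC, PROMIS-57, PGIS and symptom intensity, also without naming a covariate, and the SAP then swaps in a suitable baseline for each. Melanin may be missing from the bullets only because it has its own paragraph. This stands in part: the time-to-prodrome covariate is a literal reading, not a stated rule. It does not remove the point. The substitution clause does not reach melanin, no other sentence supplies the covariate, and fitting value and change separately would add no second treatment contrast if baseline melanin were in the model.

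A reader might also infer that the melanin analysis as a whole loses much of its precision. The documents do not support that. The listed endpoint in SAP 2.3.3 is change and percentage change. Even on the literal reading, the change model loses little at high correlation, and the large ratios belong to the raw-value model alone.

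Nor is it right that chance skin-colour differences are systematically counted as treatment effect. The error is conditional on the gap that occurs in a given trial, and the test keeps its level.

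Finally, the correlation is assumed. At 0.5 the raw-value penalty is only 15%, the same as for change.

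**Conclusion.** The point holds as a specification gap with a definite statistical cost in one of the two planned models. As written, the raw-value MMRM has no melanin baseline. Its SE is then about 1.4 to 2.3 times that of the adjusted model for r between 0.7 and 0.9 (1.15 times at 0.5), and it absorbs a chance baseline gap in proportion to r. The change model is 3% to 8% less precise over the same range (15% at 0.5). The two can disagree, and the SAP does not say which prevails.

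These sizes rest on an assumed correlation, equal SDs, a single visit, no relation between baseline time to prodrome and melanin density, and the literal reading of the covariate. Importance is minor: the endpoint is exploratory, it lies outside H1 to H12, and no primary or secondary conclusion, alpha or sample size depends on it.

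**What to change.** In the melanin paragraph of SAP 8.2.3, state that baseline six-segment average melanin density and its interaction with visit replace the baseline time-to-prodrome terms. Fit one model, and report adjusted means and adjusted change from it with the single treatment contrast they share. Use the same covariate in the melanin subgroup analyses.

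The cost is one sentence and a changed covariate in the program. A subject without a baseline reading would leave the value model, as that subject already leaves the change model. Timing should be checked, because SAP 7 describes the data review meetings for both the Week 26 and the final analysis as already held. If the change comes after unblinding, the adjusted model should be labelled post hoc.
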